7.1.10.2 Short Form-36

The SF-36 health survey is a patient-reported survey of health; it is commonly used in health economics as a variable in the quality-adjusted life year (QALY) calculation to determine the cost-effectiveness of a health treatment. The SF-36 consists of 8 scaled scores, which are the weighted sums of the questions in their section. Each scale is directly transformed into a 0 to 100 scale on the assumption that each question carries equal weight. The lower the score the more disability. The higher the score, the less disability (i.e., a score of zero is equivalent to maximum disability and a score of 100 is equivalent to no disability).

The 8 domains of the SF-36 are as follows:

- Vitality
- Physical functioning
- Bodily pain
- General health perceptions
- Physical role functioning
- Emotional role functioning
- Social role functioning
- Mental health

7.1.10.3 European Quality of Life – 5 Dimensions

The conceptual basis of the EQ-5D is the holistic view of health, including both the medical definition and the fundamental importance of independent physical, emotional, and social functioning. The concept of health in EQ-5D also encompasses both positive aspects (well-being) and negative aspects (illness).

The EQ-5D consists of a questionnaire and a VAS and is a self-rated health status. The EQ-5D records the subject's perceptions of their own current overall health, and can be used to monitor changes with time. The self-assessment questionnaire is a description of 5 dimensions (i.e., mobility, self-care, usual activities, pain/discomfort, and anxiety/depression). The subject is asked to grade their own current level of function in each dimension into 1 of 5 degrees of disability (extreme, severe, moderate, slight, or none). The combination of these with the conditions "death" and "unconscious" enables a description of 3127 different health states. Each health state can be ranked and transformed as a single score called the utility.

The EQ-5D health states may be converted into a single summary index by applying a formula that attaches values to each of the levels in each dimension. The index can be calculated by deducting the appropriate weights from 1, the value for full health (i.e., state 11111). Value sets have been derived for EQ-5D in several countries using the European Quality of Life-5 Dimensions Visual Analog Scale (EQ-5D VAS) valuation technique or the time trade-off valuation technique.

7.1.10.4 Work Productivity Survey – Rheumatoid Arthritis

The WPS-RA measures the impact of RA and treatment on subject productivity within and outside the home during the previous month. It contains 9 questions addressing employment status, productivity within and outside the home, and daily activities. One item of the WPS-RA addresses current labor market participation. This is a strong indicator of work ability because not working implies complete loss of paid productivity. There are also normative and comparative data available on employment status. Two items capture self-reported work absences due to arthritis, and 2 items capture the same concept but applied to non-paid work. These are separated into full and partial days (i.e., days of work missed and days with productivity reduced by at least half). Additional items capture the respondent's estimate of the extent to which arthritis has interfered with the subject's work productivity (paid and non-paid) on a scale of 0 to 10, the number of days in the last month outside help was hired because of arthritis, and the number of days in the last month family, social, or leisure activities were missed because of arthritis.

7.1.10.5 Functional Assessment of Chronic Illness Therapy – Fatigue Scale

FACIT-Fatigue is a 13-item tool that measures an individual's level of fatigue during their usual daily activities during the most recent week. The level of fatigue is measured on a 4-point Likert scale.

The sum of the scoring (total score) will be used for the statistical evaluation. If an item is not scored, the total score will be set to missing.

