4.2 Efficacy Endpoints

For the efficacy endpoints, comparison will be made with Core Baseline values (i.e., Week 0 baseline values in the core study) and OLE Baseline values (i.e., Week 24 baseline values in the OLE study) for most parameters, as defined in Section 9.4.1. For subjects from Study CL04041025 who initiate OKZ treatment at Week 16 of the core study after having completed 16 weeks of placebo treatment, changes from the last pre-OKZ value will also be summarized.

The following efficacy endpoints will be evaluated:

- Proportion of subjects achieving an ACR20, ACR50, and ACR70 response who remain on randomized open-label treatment and in the study, assessed at all applicable time points
- Proportion of subjects with Simplified Disease Activity Index (SDAI) ≤3.3 remission, who remain on randomized open-label treatment and in the study, assessed at all applicable time points

- Proportion of subjects with Disease Activity Score 28-joint count (DAS28) low
 disease activity (based on DAS28 C-reactive protein [CRP] <3.2), who remain on
 randomized open-label treatment and in the study, assessed at all applicable time
 points
- Change from baseline over time in DAS28 (CRP), assessed at all applicable time points
- Change from baseline over time in the measure of physical ability based on Health Assessment Questionnaire-Disability Index (HAQ-DI), assessed at all applicable time points
- Proportion of subjects with improvement from baseline in HAQ-DI score ≥0.22, who
 remain on randomized open-label treatment and in the study, assessed at all applicable
 time points
- Change from baseline over time in the scores for the following patient-reported outcomes (PRO) measures, assessed at all applicable time points:
- Short Form-36 (SF-36) Physical Component Summary (PCS) and Mental Component Summary (MCS) total scores
- European Quality of Life-5 Dimensions (EQ-5D)
- Work Productivity Survey-Rheumatoid Arthritis (WPS-RA)
- Functional Assessment of Chronic Illness Therapy-Fatigue Scale (FACIT-Fatigue)
- Change from baseline over time in SDAI and Clinical Disease Activity Index (CDAI), assessed at all applicable time points

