7.1.10.1 Health Assessment Questionnaire – Disability Index

The HAQ-DI is a patient-reported questionnaire that provides an assessment of the impact of the disease and its treatment on physical function. The HAQ-DI assesses the degree of difficulty experienced in 8 domains of daily living activities using 20 questions. The domains are dressing and grooming, arising, eating, walking, hygiene, reach, grip, and common daily activities, and each domain (activity) consists of 2 or 3 items. For each question, the level of difficulty is scored from 0 to 3 where 0 = without any difficulty, 1 = with some difficulty, 2 = much difficulty, and 3 = unable to do. Each category is given a score by taking the maximum score of each question (i.e., question in each category with the highest score for that category).

If the maximum score is 0 or 1, but a device related to that category is used, or help from another person is provided for the category, then the category score is increased to 2. If the category score is already a 2 (or above), the score in that category remains 2 with or without any aids or device use. If the subject does not provide an answer for any questions within a category, no score will be provided for that category. The HAQ-DI will be calculated by dividing the sum of the category scores by the number of categories with at least 1 question answered. If fewer than 6 categories have responses, no disability score will be calculated.

The HAQ-DI will also include patient assessments of pain and health on a scale of 0 to 100.

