9.4.8 Handling of Missing Data

Missing efficacy data resulting from missed intermediate visits will be imputed from the surrounding visits. For binary efficacy endpoints, if the status at visits both before and after the missed visit is classified as responder, the subject will be considered a responder at the missed visit. Otherwise, the subject will be considered a nonresponder. If an assessment for a given binary endpoint at the last visit is missing for a completing subject, data from the 2 previous visits will be used with the same logic for determining the response status. For the ACR20/50/70 endpoints, if only some components of the response criteria are missing but the available components allow classifying the subject as a responder, the responder category will be used. Otherwise, the method based on surrounding visits as described above will be applied. Similarly, for all continuous endpoints, an average of values from the surrounding visits will be imputed for the missing visit.

Missing efficacy data resulting from early treatment discontinuation will not be imputed.

Missing safety data will not be imputed.

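### One blank item out of 13 voids the FACIT-Fatigue total, and the plan does not say whether that visit is then left missing or imputed

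*Combined protocol and SAP*

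**What the plan says.** Section 7.1.10.5 describes the instrument: "FACIT-Fatigue is a 13-item tool that measures an individual's level of fatigue during their usual daily activities during the most recent week". On scoring it says "The sum of the scoring (total score) will be used for the statistical evaluation", followed by "If an item is not scored, the total score will be set to missing". It sets no minimum number of answered items and does not scale up a partial sum. Section 4.2 lists change from baseline in FACIT-Fatigue among the efficacy endpoints.

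Two other multi-part measures in the protocol tolerate gaps:

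- **HAQ-DI (Section 7.1.10.1).** There are eight categories, and a category counts once one of its questions is answered. The sum is divided by the number of answered categories. The limit is "If fewer than 6 categories have responses, no disability score will be calculated".
- **Joint counts (Section 7.1.2).** When some joints cannot be assessed, the count is weighted by the number that can.

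On missing data, Section 9.4.8 opens with "Missing efficacy data resulting from missed intermediate visits will be imputed from the surrounding visits". After rules for binary endpoints and for partly missing ACR components it adds: "Similarly, for all continuous endpoints, an average of values from the surrounding visits will be imputed for the missing visit". Data missing because of early treatment discontinuation are not imputed. Under Section 9.4.1, OLE Baseline is the last value available before the first OLE dose.

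**The concern.** The rule treats a form with one skipped question like a form never filled in. Twelve same-day answers say far more about that day's fatigue than nothing does, and more than scores from months earlier and later. The protocol accepts this principle for HAQ-DI and joint counts and gives no reason for departing from it here.

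The plan also leaves the consequence open. If a voided total stays missing, usable data are lost and the visit summaries are less precise. If it is imputed from neighbouring visits, the same information is lost and the subject's course is smoothed as well. A form voided at Week 24 has a further effect: OLE Baseline falls back to an older core-study value, if there is one, and that value enters every later change from OLE Baseline.

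**Working it through.** The documents state no missing-data figure for FACIT-Fatigue, so there is nothing to reproduce. The check has four steps.

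**1. Share of forms lost.** Inputs: 13 items (Section 7.1.10.5); item-blank rate *p* (assumed); about 1880 subjects (Section 9.1), used only for scale and ignoring dropout. With independent blanks:

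- forms lost = 1 − (1 − p)^13
- share of lost forms with exactly one blank = 13p(1 − p)^12 / [1 − (1 − p)^13]
- limits for any pattern of blanks: from *p* (all blanks fall on the same forms) to 13*p* (no form has more than one)

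| p (assumed) | Forms lost, independent blanks | Of 1880 | Lost forms with one blank | Limits |
|---|---|---|---|---|
| 0.5% | 1 − 0.995^13 = 6.3% | 119 | 97% | 0.5% to 6.5% |
| 1% | 1 − 0.99^13 = 12.2% | 230 | 94% | 1% to 13% |
| 2% | 1 − 0.98^13 = 23.1% | 434 | 88% | 2% to 26% |

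The independence figures lie near the upper limit. At the lower limit the lost forms are wholly blank, and proration could not rescue them.

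**2. Precision if voided totals stay missing.** The standard error of a visit mean grows by 1/√(1 − share lost): 1/√0.937 = 1.03, 1/√0.878 = 1.07 and 1/√0.769 = 1.14 for the three rows.

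**3. Distance of the neighbours if voided totals are imputed.** Table 1 schedules FACIT-Fatigue at Weeks 24, 36, 52, 64, 76, 88 and 106.

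| Voided week | Neighbours | Gaps (weeks) |
|---|---|---|
| 36 | 24, 52 | 12, 16 |
| 52 | 36, 64 | 16, 12 |
| 64 | 52, 76 | 12, 12 |
| 76 | 64, 88 | 12, 12 |
| 88 | 76, 106 | 12, 18 |

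This covers Weeks 36 to 88 only. The last-visit rule in Section 9.4.8 is written for binary endpoints, so Week 106 has no continuous rule, and OLE Baseline takes the last available value.

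**4. Error of each substitute, in SDs of the total (all correlations assumed).**

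- Average of two neighbours: √(1 + (1 + ρ₁₃)/2 − 2ρ₁₂), where ρ₁₂ is the adjacent-visit correlation and ρ₁₃ that between the two neighbours. With (0.5, 0.4) it is √0.70 = 0.84; with (0.8, 0.7) it is √0.25 = 0.50.
- Proration from 12 of 13 items, with equal item means and variances and inter-item correlation *r*: √[(1 − r)(1 + 1/12) / (13(1 + 12r))]. At r = 0.3 it is 0.11; at r = 0.5 it is 0.08.

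Over these ranges the neighbour average is about 4 to 11 times less accurate.

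**The case against.** The strongest objection concerns imputation. A reader might infer that voided forms are replaced by averages of visits months away, and that the endpoint is therefore biased toward smooth trajectories. The documents do not establish this. Sections 9.4.7 and 9.4.8 tie imputation to missed visits, and a skipped item on a form completed at an attended visit is not a missed visit. Partly missing components are addressed for ACR only. The imputation reading is possible, because the ACR rule sends unresolved partial data to the surrounding-visit method and the next sentence extends to all continuous endpoints. It is not written, however, so the smoothing effect is conditional. The loss of information holds on either reading.

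Other points on that side:

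- **Size.** Item-blank rates are not in the documents, and the formula also assumes independence. Questionnaires come first at each visit (Section 5.4), and Section 7.4.5.1 refers to site review of them; both may keep blanks rare. This stands, and the percentages are illustrations.
- **HAQ-DI.** It is a mean over categories and FACIT-Fatigue is a sum, so different rules do not contradict each other. This stands. The comparison shows only that the protocol already accepts proration.
- **Strict scoring has a purpose.** It avoids assuming that a skipped item resembles the answered ones, and it may match core-study scoring, which is not shown here. Both are real considerations, so it cannot be said that the rule gains nothing. Neither justifies discarding 12 answers for one blank.

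**Conclusion.** The point holds as a scoring weakness with an undefined consequence. The all-items rule discards nearly complete forms, and the plan does not say whether the resulting totals are left missing or imputed. The loss per visit is 6%, 12% or 23% at item-blank rates of 0.5%, 1% or 2%. This rests on assumed rates and independent blanks, and it is lower if blanks cluster. The comparison of errors rests on assumed correlations.

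The importance is low. FACIT-Fatigue is one of several patient-reported endpoints, and Section 9.4 makes all analyses descriptive. What is affected is the precision of this endpoint and, where a Week 24 form is voided, the age of the OLE Baseline value. A general bias toward smooth trajectories should not be claimed.

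**What to change.** 1. In Section 7.1.10.5 and the SAP, replace the rule with a prorated total, 13 × (sum of answered items / number answered), when a stated minimum is answered, and set it to missing otherwise. The proposed minimum is 7 of 13. That threshold is not in the documents and should be checked against the instrument's scoring instructions.
2. In Section 9.4.8, state how totals still missing at attended visits are handled, including at Week 106. Leaving them missing would fit the section's present scope of missed visits.

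The cost is a short text change in each place, made before the SAP is finalised ahead of database lock (Section 9.4). If the core studies scored strictly, the core-study totals used as baseline must be re-derived by the same rule. Proration also assumes that a skipped item resembles the mean of the answered ones; with a single blank that assumption affects one thirteenth of the total.

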7.2 Pharmacokinetics

There will be no collection of blood samples for the determination of OKZ concentration in plasma in this study.

• The Week 24 sample is the last sample to be collected in the core studies. This sample must be collected prior to administration of OKZ in the OLE study, and the sample will be analyzed and included in the data set of the core study in which the subject participated, according to the procedures detailed in the core study protocol. This sample will not be analyzed as part of the OLE data set.

To provide documentation that the Week 24 PK sample was collected prior to the first dose of study treatment in this study, the date and time of OKZ administration at Week 24 will be captured in each subject's eCRF.

Although there will be no collection of blood samples in this study for the determination of OKZ concentration in plasma, blood samples that are collected for immunogenicity analysis (see Section 7.3) may also be used to determine OKZ concentrations in plasma if it is

determined that such evaluation may provide additional information regarding subject safety and efficacy of OKZ (e.g., due to unexpected immunogenicity results).

7.3 Immunogenicity

Immunogenicity will be assessed by evaluating the impact of ADAs on subject safety and efficacy of OKZ. Blood samples for analysis of the incidence and titer of antibodies to OKZ and the incidence of any neutralizing antibodies to OKZ in plasma will be collected at the times shown in Table 1.

The actual sample collection date and exact time will be entered on the Immunogenicity Blood Collection eCRF page. Sampling problems will be noted in the Comments section of the eCRF. All blood samples will be taken by either direct venipuncture or an indwelling cannula inserted in a forearm vein. A Laboratory Manual will be provided to the Investigator with detailed information on sample collection, handling, and shipment of the ADA samples. Tubes and preprinted labels will be provided by the central laboratory to the study sites.

Antidrug antibody samples from all subjects who received OKZ will be analyzed, using appropriately validated methods, by R-Pharm International or R-Pharm International's designee. Samples will initially be screened for antibodies. A confirmation assay will be used to confirm the positive status for samples that scored potentially positive by the Screening assay. In confirmed positive samples, the relative titer of the antibody will be determined as well as whether the confirmed positive sample represents a neutralizing antibody.

7.4 Safety

Safety assessments will consist of monitoring and recording all AEs, including SAEs, nonserious AESIs, and pregnancies; measurement of safety laboratory assessments; measurement of vital signs, ECGs, physical examinations; and other tests that are deemed critical to the safety evaluation of the study in all subjects who receive at least 1 dose of study treatment. As discussed in Section 7.4.2.3, any pregnancy that occurs while a subject is enrolled in the study will also be monitored and reported according to the appropriate regulations.

The Investigator remains responsible for following, through an appropriate health care option, AEs that are serious and nonserious that caused the subject to discontinue before completing the study. Any AE, including any AE still ongoing at the end of the study, should be followed until it has resolved, it has a stable sequelae, the Investigator determines that it is no longer clinically significant, or the subject is lost to follow-up. If no follow-up is provided, the Investigator must provide a justification.

In addition to records of observations made at specific times, unexpected signs and symptoms and concomitant medications will be recorded in the clinical study records throughout the study. The Investigator will also collect completed pages of the Subject Diary (see Section 5.5) at Visits 2 (Week 26) through 10 (EoT/Week 106), and the Investigator will review any complaints, signs, or symptoms experienced by the subject in association with administration of study treatment. Completed pages of the Subject Diary will serve as source documents, and information will be recorded on the appropriate pages of the eCRF. The Subject Diary will not be used during the Safety Follow-Up Period. Further routine medical assessments in addition to those specified in Table 1 may take place during the study as clinically indicated (e.g., chest X-rays to investigate lung lesions, ECG, etc).

Safety measures in this study include, but are not limited to, SAEs, AEs, vital signs, body weight, and laboratory evaluations, and if required, this information must be present in the AE/SAE report made by the Investigator.

7.4.1 Adverse Events

For the purposes of this study, an AE will be defined as any untoward medical occurrence in a subject or clinical investigation subject administered a pharmaceutical product and which does not necessarily have a causal relationship with this treatment. An AE can therefore be any of the following:

- Any unfavorable and unintended sign, symptom, or disease temporally associated with the use of a medicinal product, whether or not considered related to the medicinal product.
- If the Investigator determines a laboratory abnormality to be clinically significant, it is considered a laboratory AE; however, if the abnormal laboratory value is consistent with a current diagnosis (or signs or symptoms if a diagnosis is not possible) and is not a clinically significant worsening from the baseline laboratory parameter, it should be documented accordingly without being reported as a separate laboratory AE.
- Any new disease or exacerbation of an existing disease (a worsening in the character, frequency, or severity of a known condition).

The Investigator is responsible for recording all AEs observed during the study starting at Visit 1 (OLE Baseline/Week 24). All AEs are recorded throughout the study until the last visit of the subject. The Investigator is responsible for the appropriate medical care of the subjects during the entire study.

Each AE is to be evaluated for duration, severity, seriousness, and causal relationship to the investigational drug. For all AEs, the Investigator must pursue and obtain information adequate both to determine the outcome of the AE and to assess whether it meets the criteria for classification as an SAE. The Investigator is required to assess causality as described below.

Severity

The severity of AEs will be characterized according to the CTCAE grades and definitions summarized in Table 4.

Table 4 CTCAE Grades and Corresponding AE Severity

CTCAE Grade	Corresponding AE Severity
Grade 1	Mild; asymptomatic or mild symptoms; clinical or diagnostic observations only; intervention not indicated
Grade 2	Moderate; minimal, local, or noninvasive intervention indicated; limiting age-appropriate instrumental ADL
Grade 3	Severe or medically significant but not immediately life-threatening; hospitalization or prolongation of hospitalization indicated; disabling; limiting self-care ADL
Grade 4	Life-threatening consequences; urgent intervention indicated
Grade 5	Death related to AE

Abbreviations: ADL = activities of daily living; AE = adverse event; CTCAE = Common Terminology Criteria for Adverse Events.

Causality Assessment

The Investigator is responsible for making an assessment of the causal relationship between the study treatment and the AE. Investigators should use their knowledge of the subject, the circumstances surrounding the event, and an evaluation of any potential alternative causes to determine whether or not an AE is considered to be related to the study treatment. The causal relationship between the study treatment and the AE must be characterized as "related" or "not related". The following guidance should be taken into consideration:

- Temporal relationship of event onset to the initiation of the study treatment.
- Course of the event, considering especially the effects of dose reduction, discontinuation of the study treatment, or reintroduction of the study treatment.
- Known association of the event with the study treatment, or with similar treatments.
- Known association of the event with the disease under study.

- Presence of risk factors in the subject or use of concomitant medications known to increase the occurrence of the event.
- Presence of non-treatment-related factors that are known to be associated with the occurrence of the event.

The Investigator should report the relatedness of each event based on the most likely causal relationship, and the study site staff is responsible for obtaining any missing information.

